7.4.5.8 Chemosis

It is defined as conjunctival edema resulting from an inflammatory reaction. It is graded as present or absent. The evaluator will use a narrow 60° beam of light and measure whether the conjunctiva separates from the sclera by $\geq 1/3$ of the entire eyelid opening or whether it extends beyond the gray line. [40]

Management as AE: The presence of chemosis will be considered an adverse event.

7.4.5.9 Adverse events

As described in subsection 8.2 Definition of Adverse Event , an adverse event is defined as Any adverse medical occurrence in a subject to whom an investigational product is administered, regardless of causal attribution.

The management of adverse events will be carried out in accordance with the provisions of Section 8. Evaluation and management of adverse events and incidents.

The Principal Investigator will record any adverse events that may occur in the study subjects in the corresponding section of the eCRF and will also report them in the clinical record.

For an adequate assessment of adverse events, in addition to the targeted questioning, a Comprehensive Ophthalmologic Evaluation must be performed at each visit . This evaluation consists of: ophthalmologic examination of the eyelids and adnexa; anterior and posterior segments, which are performed during a routine ophthalmologic examination, procedures not specifically included in the study variables. The posterior pole evaluation may be performed with direct or indirect ophthalmoscopy, with or without pharmacological mydriasis, at the discretion of the PI. The fundus will be assessed for abnormalities that could alter the study results. IOP will be measured during this evaluation, using the PI's chosen instrument, and should be measured after the stain evaluation. The results of the evaluation will be recorded in the clinical record. Only those findings that the Principal Investigator considers to be adverse events will be reported in the eCRF

Adverse events that may occur with PRO-185 are: ocular burning, ocular hyperemia, foreign body sensation, itching, red eye, eye irritation, tearing, little relief of discomfort, blurred vision, burning, superficial punctate keratitis, stinging, mydriasis, increase or decrease in intraocular pressure, release of pigment granules, rebound hyperemia, headache, vertigo, hypertension, hypotension, cardiac irregularities (including tachycardia, bradycardia, among other types of cardiac irregularities), nervousness or excitability, nausea, dizziness, weakness, drowsiness and diaphoresis. [29]

7.4.5.10 Respiratory rate

This is the measurement of the number of breaths per minute taken by research subjects. It is assessed discreetly by observing, without the subject's awareness, the movements of the rib cage, counting each rise/rise of the subject's rib cage as one breath. A range of 12 to 24 breaths per minute is considered normal.

Management as an AE: Any abnormal value will be considered an adverse event. In some cases, the research subject may need to be considered a possible case of COVID-19, and the investigator may need to refer the patient for medical care and withdraw the subject from the research.

7.4.5.11 Body temperature

It is the temperature level of a body. Normal values range from 35°C to 37.4°C. It can be measured using a contact or non-contact thermometer on different parts of the body. Any thermometer calibrated at the research center may be used in the study, as long as the same one is used for all patients and for all their visits.

Management as an AE: Any abnormal value will be considered an adverse event. In some cases, the research subject may need to be considered a possible case of COVID-19, and the investigator may need to refer the patient for medical care and withdraw the subject from the research.

7.5 Description of the procedures or assessments during the study

The various procedures that will be performed during the study are described below. The list may not be in order and could be arranged in the most optimal way according to the needs of the research center.

7.5.1 Signature of informed consent

Procedure that ensures that the research subject has voluntarily expressed his or her intention to participate in this research, after having understood the information given to him or her about the objectives of this research, benefits, discomforts, and possible risks.

7.5.2 Taking a medical history (including ophthalmological and general medical history)

This includes questions about medical history, symptoms, or diagnosed conditions, as well as any medications currently being used, regardless of their route of administration. It includes measurements of body weight and height (somatometry), and a complete ophthalmological evaluation.

7.5.3 Eligibility criteria

It is the evaluation that the patient meets all the inclusion criteria and none of the exclusion or elimination criteria.

7.5.4 Subject code assignment

It is the granting of a code that represents the subject in the study. This code is assigned when the research subject is included in the study.

7.5.5 Adverse events

Described in section 7.4.5.9 Adverse events.

7.5.6 Measuring vital signs

This involves measuring heart rate, respiratory rate, blood pressure, and body temperature. These measurements can be performed with a stethoscope, sphygmomanometer, and mercury or digital thermometer.

Vital signs are described in sections 7.4.5.2, 7.4.5.3, 7.4.5.10 and 7.4.5.11.

7.5.7 Urine pregnancy test

Pregnancy testing will be performed at the baseline and final visits. The researcher must provide the research subject with a female, reproductive-age subject (no natural or induced menopause, defined as 12 consecutive months of amenorrhea) [41]. The patient will be allowed to go to the bathroom and have privacy for the test. After the test is performed, the researcher must verify the result by observing the medical device.

7.5.8 Ophthalmological evaluation

Evaluation of the eyeball, eyelids, eyelashes, and other ocular structures through inspection, slit lamp (biomicroscopy), and palpation (touch). This evaluation includes best-corrected visual acuity, assessment of the integrity of the ocular surface, anterior segment, intraocular pressure, and gonioscopy and posterior segment (fundoscopy).

7.5.8.1 Best-corrected visual acuity

Described in section 7.4.5.6 Best corrected visual acuity.

7.5.8.2 Integrity of the ocular surface

This will be performed using biomicroscopy using the research center's slit lamp. The cornea, conjunctiva, and tear film will be inspected, and ocular staining will be performed with lissamine green and fluorescein (the stains are described in section 7.4.5.7).

7.5.8.3 Anterior segment

This is the evaluation of the anterior segment structures (cornea, conjunctiva, anterior chamber, iris, pupil (including measurement of pupillary diameter), lens, aqueous humor). The evaluation will be performed using a slit lamp.

7.5.8.4 Intraocular pressure

Described in section 7.4.5.1 Intraocular pressure.

7.5.8.5 Gonioscopy

This is the assessment of the iridotrabecular angle by attaching a gonioscopy lens to the patient's cornea. In some cases, the lens will be filled with a gel to improve its fit with the patient's cornea.

The Shaffer system will be used for angle classification.

Table iv. Shaffer classification

Degree	Angular opening	Description	Risk of occlusion
4	45°-35°	Open	Impossible
3	35°-20°	Open	Impossible
2	20°	Narrow	Possible
1	≤ 10°	Extremely narrow	Likely
0	0°	Closed	Occluded

Angle closure or suspected angle closure will be considered if Grade 2 or less is present in more than 180° of the angular circumference.

7.5.8.2 Posterior Segment (fundoscopy)

Also called ophthalmoscopy, this is an examination performed with a light and magnifying glass to observe the fundus (optic nerve and retina) through the pupil. Sometimes, the pupil will need to be dilated to allow a better evaluation of the fundus.

7.5.9 Applying medication during visits

During patient visits, various medications or medical devices may be applied to the ocular surface for ophthalmological examination.

Examples:

- Tetracaine 0.5% ophthalmic solution, used to anesthetize the patient and facilitate measurement of intraocular pressure, application of dyes for staining, and placement of the gonioscopy lens.
- Ophthalmic solution of 0.8% tropicamide and 5% phenylephrine, used to dilate the pupil and better assess the posterior segment.
- PRO-185 ophthalmic solution, an investigational drug, applied at visits 1 and 2.
- Hypromellose 2% ophthalmic solution may be used by the Researcher for gonioscopy assessment.

7.5.10 Delivery of material for the subject

This refers to the provision of the subject's ID card and the subject's diary. The ID card will serve as identification with the treatment assignment number; this card can also serve as an appointment card. The Subject's Diary is used to record the number of times the treatment is administered.

7.5.11 Delivery of the study medication

Once the patient is in the study, the investigational product will be given to them, and the dosage will be explained (one drop four times a day in both eyes).

7.5.12 Evaluation of concomitant medications

This question asks about any medications you are currently taking regularly or have used in the past month. If you have required medication therapy injected into the eye, you should be asked about any medications you have injected in the past 6 months.

7.5.13 Assessment of treatment adherence

This refers to indirectly assessing the number of applications during the period between visits. To assess the approximate number of drops, the medication dropper bottle (concomitant or investigational treatment) can be weighed. The Subject Diary is also reviewed to determine the recorded applications.

7.5.14 Return of study medication

It refers to the return of the product under investigation by the research subject.

7.5.15 Withdrawal from the subject's journal

It refers to the delivery of the subject's diary by the research subject.

7.6 Diagram and schedule of study activities

7.6.1 Study diagram

Figure 3Study diagram

7.6.2 Study activity schedule

Table v. Study schedule

Procedures	Baseline visit		Visit 1		Visit 2		Final visit
	Day 1		Day 3 (+1)		Day 8		Day 10 (+1)
	Pre-TP	Post -	Pre -	Post-	Pre -	Post-	Without
	TP	Tx	Tx	Tx	Tx	Tx	treatment
FCI Signature	X						
Medical record	X						
Eligibility criteria	X						
Subject code assignment	X						
Adverse events	X	X	X	X	X	X	X
Heart rate	X	X	X	X	X	X	X
Respiratory rate	X		X		X		X
Blood pressure	X	X	X	X	X	X	X
Temperature (°C)	X		X		X		X
Urine pregnancy test	X						X
AVMC	X		X		X		X
Anterior segment evaluation	X	X	X	X	X	X	X
Pupillary diameter measurement	X	X	X	X	X	X	X
Eye stains	X	X	X	X	X	X	X
Intraocular pressure	X	X	X	X	X	X	X
Gonioscopy	X						
Pharmacological mydriasis (phenylephrine/tropicamide)	X						
Evaluation of the posterior segment	X		X		X		X
Application of PRO-185 during a visit			X		X		
Delivery of material for the subject		X					
Delivery of the study medication		X					

Procedures	Baseline visit		Visit 1		Visit 2		Final visit
	Day 1		Day 3 (+1)		Day 8		Day 10 (+1)
	Pre-TP	Post -	Pre -	Post-	Pre -	Post-	Without
	TP	Tx	Tx	Tx	Tx	Tx	treatment
Evaluation of concomitant medications	X		X		X		X
Adherence assessment			X		X		
Return of study medication						X	
Withdrawal from the subject's diary						X	

PRE-TP: prior to application of 0.8% tropicamide and 5% phenylephrine ophthalmic solution (TP Ofteno[®]), indicates that the checks will be performed prior to pharmacological mydriasis. Post-TP: post application of the TP Ofteno[®] solution, indicates that the checks will be performed with pharmacological mydriasis. Pre- Tx : pretreatment, indicates the checks to be performed before the application of the investigational medicinal product. Post-Tx : post-treatment, indicates the evaluations to be performed within 20-40 minutes after the application of the investigational medicinal product. ICF: informed consent form. BCVA: best corrected visual acuity.

7.7 Procedures to be performed per visit

The procedures to be performed at each visit are listed below; these may not be in the optimal order for the Research Center. The researcher should organize them according to their needs, and the needs of the study and sponsor.

In assessing treatment adherence, the subject's diary may be reviewed and/or the dispensed dropper bottles may be weighed.

7.7.1 Baseline visit

- Consent signature informed
- General and ophthalmological clinical history taking
- Measurement of vital signs (temperature, blood pressure, heart rate, respiratory rate)
- Drug evaluation concomitants
- Measurement of best-corrected visual acuity
- Ophthalmological evaluation (before and after pupil dilation)
- Evaluation of pupil diameter
- Ocular staining with fluorescein and lissamine green
- Measurement of intraocular pressure
- Gonioscopy
- Review of eligibility criteria
- Event evaluation adverse
- Pupil dilation
- Delivery of the investigational product

7.7.2 Visit 1

- Pre-application procedures for the investigational product
 - o Measurement of vital signs (temperature, blood pressure, heart rate, respiratory rate)
 - o Drug evaluation concomitants
 - o Measurement of best-corrected visual acuity
 - o Assessment ophthalmological
 - o Evaluation of pupil diameter
 - o Ocular staining with fluorescein and lissamine green
 - o Measurement of intraocular pressure
 - o Review of continuation criteria
 - o Event evaluation adverse
- Post-application procedures for the investigational product
 - o Measurement of vital signs (blood pressure and heart rate)
 - o Measurement of best-corrected visual acuity
 - o Assessment ophthalmological
 - o Evaluation of pupil diameter
 - o Ocular staining with fluorescein and lissamine green
 - o Measurement of intraocular pressure
 - o Review of continuation criteria
 - o Event evaluation adverse

7.7.3 Visit 2

- Pre-application procedures for the investigational product
 - o Measurement of vital signs (temperature, blood pressure, heart rate, respiratory rate)
 - o Drug evaluation concomitants
 - o Measurement of best-corrected visual acuity
 - o Assessment ophthalmological
 - o Evaluation of pupil diameter
 - o Ocular staining with fluorescein and lissamine green
 - o Measurement of intraocular pressure
 - o Review of continuation criteria
 - o Event evaluation adverse
- Post-application procedures for the investigational product
 - o Measurement of vital signs (blood pressure and heart rate)
 - o Measurement of best-corrected visual acuity
 - o Assessment ophthalmological
 - o Evaluation of pupil diameter
 - o Ocular staining with fluorescein and lissamine green
 - o Measurement of intraocular pressure
 - o Review of continuation criteria
 - o Event evaluation adverse
 - o Return of the research product

- Return of the subject's diary

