2.5 Risk-benefit evaluation

2.5.1 Known potential risks

Formulations containing naphazoline and/or hypromellose at the same concentrations as PRO-185 are available over-the-counter without the need for clinical or preclinical studies in high surveillance countries.[11] The risks associated with the use of this product in specific populations are described below; however, the use of this medication in the study will be in a population group without the alterations or characteristics described below.

Patients with high blood pressure, cardiovascular abnormalities, hyperglycemia, hyperthyroidism, infections, and corneal wounds should use products containing naphazoline with caution due to the risk of aggravation of these conditions.[29]

Patients with angle-closure glaucoma or closed angles may experience significant increases in intraocular pressure and should not use products similar to PRO-185.[29] [30] [31]

Overuse of this product may cause rebound conjunctival hyperemia.[29] [11]

Some patients, when using this product as recommended, may experience pharmacological mydriasis, with the resulting decreased vision.[11]

Ophthalmic vasoconstrictors, such as this product, should not be used in children under 12 years of age, and serious reactions requiring hospitalization have been reported with accidental ingestion of naphazoline products by children.[29] [32]

Administration of this product during pregnancy and lactation is prohibited.[29] [32]

Although menthol is present as one of the components, it is an excipient and is present at a concentration 80 times lower than the concentration that demonstrated mild irritation in repeated-dose irritability tests, and 10 times lower than the lowest concentration that demonstrated no irritating effects. Therefore, no additional safety data are expected from incorporating it as an excipient in the PRO-185 formulation. Furthermore, there is already experience in other markets with the use of eye drops with menthol as an excipient, and a lubricant and vasoconstrictor.[25]

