7.4.2 Secondary outcome variables

- Best corrected visual acuity (BCVA).
- Changes in ocular surface staining.
- Incidence of chemosis.
- Incidence of expected adverse events.
- Incidence of unexpected adverse events.

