7.4.5.6 Best-corrected visual acuity

Visual acuity (VA) is a test of visual function. Spatial visual acuity is the ability to distinguish separate elements of an object and identify them as a whole. It is quantified as the minimum angle of

separation (located at the nodal point of the eye) between two objects that allows them to be perceived as separate objects.

Snellen notation is described as the distance at which the test is performed divided by the distance at which the letter is vertically equivalent to 5 minutes of arc. Thus, at 6 meters a letter 6/6 (20/20) is equivalent to 5 minutes of arc, a letter 6/12 (20/40) is equivalent to 10 minutes, and a letter 6/60 (20/200) is equivalent to 50 minutes. The Snellen fraction can also be expressed as a decimal (i.e. 20/20 = 1 and 20/40 = 0.5).[34]

VA will be assessed at baseline, without refractive correction, using the Snellen chart. This chart will be placed in a location with adequate natural or artificial lighting and at a distance of 3 m from the subject being assessed. Visual acuity will be measured in the study eye, asking the subject to keep both eyes open and using an occluder to cover the contralateral eye. The subject will read aloud the lines indicated by the evaluator. The line with the smallest letters visible will be recorded by the evaluator as a fraction of the OD VA in the clinical record.

The subject's best refractive correction will then be performed, and the examination will be repeated using the obtained refraction. This result will be reported as best-corrected visual acuity, recorded as a fraction and decimal in both the clinical record and the eCRF .

Management as AE: A decrease of 2 or more lines of vision in BCVA compared to that obtained at the baseline visit will be considered an adverse event.

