10.3.2.2 Analysis for secondary variables

For the analysis of these variables, the same primary analysis will be performed as long as the necessary measurements are available.

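### Visual acuity after the drop at visits 1 and 2 is listed in the visit procedures but in none of the three schedules, so its collection, and the pre/post contrast that needs it, is uncertain

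*Protocol*

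**What the plan says.** Best-corrected visual acuity (BCVA) is a secondary outcome (Protocol 7.4.2).

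**Visit procedures.** Protocol 7.7.2 and 7.7.3 each have a pre-application list and a second list headed "Post-application procedures for the investigational product". The item "Measurement of best-corrected visual acuity" stands in both lists at both visits.

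**Schedules.** Protocol 1.3, Protocol Table v (7.6.2) and SAP Table 1 agree with each other. BCVA (row AVMC) is marked once at baseline, then at visit 1 Pre-Tx, visit 2 Pre-Tx and the final visit. Both Post-Tx cells are blank. The table notes define Post-Tx; in Table v it "indicates the evaluations to be performed within 20-40 minutes after the application of the investigational medicinal product".

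**Analysis.** For secondary variables, Protocol 10.3.2.2 states that "the same primary analysis will be performed as long as the necessary measurements are available". The primary analysis in 10.3.2.1 is the before/after difference at visits 1 and 2, plus baseline against the final visit. Section 10.4 plans no imputation.

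**Clinical background.** Protocol 2.5.1 says that some users "may experience pharmacological mydriasis, with the resulting decreased vision". Section 7.4.5.6 makes a loss of two or more lines from the baseline visit an adverse event.

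**The concern.** Two parts of the same protocol give the site different instructions for a named safety outcome, and the SAP repeats only one of them. No text ranks the visit lists above the schedules or the reverse.

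Timing makes this more than a clerical matter. Under Protocol 6.1.3 the first dose follows the end of the baseline visit, subjects come to visits 1 and 2 without having used the product beforehand, and no product is used after visit 2. The final visit is without treatment. On the schedules, then, each of the four BCVA readings falls before the visit's drop or off treatment. The reading most relevant to the visual effect named in 2.5.1 is the one in dispute.

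The clause on available measurements in 10.3.2.2 adds to this. If the readings are not taken, the visit 1 and visit 2 contrast can drop out with no deviation recorded and no reason given.

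**Working it through.** The plan states no figure on this point, so there is none to reproduce. The check is to set the sources side by side and count.

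**Step 1. Where BCVA is required.**

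| Source | Baseline | V1 before drop | V1 after drop | V2 before drop | V2 after drop | Final | Readings per subject |
|---|---|---|---|---|---|---|---|
| Protocol 7.7.1 to 7.7.4 | yes | yes | yes | yes | yes | yes | 6 |
| Protocol 1.3, Table v, SAP Table 1 | yes | yes | no | yes | no | yes | 4 |

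**Step 2. Are the blank cells real?** In the same Table v, the intraocular pressure row reads "Intraocular pressure X X X X X X X": all seven columns are filled, as they are for heart rate. The respiratory rate row has the same four marks as BCVA, and 7.7 lists respiratory rate only before application, so for that variable the two sources agree. BCVA has the same row pattern, but 7.7 contradicts it. The blanks are therefore genuine entries.

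**Step 3. Is the post-application item in 7.7 a blind copy?** The post-application lists leave out temperature, respiratory rate and concomitant medication, as the schedules do, but keep BCVA. They also list an ophthalmological evaluation, which 7.5.8 defines as including BCVA. The item was not simply carried over with everything else.

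**Step 4. Count the data.** The input is the planned N = 22 (Synopsis; 10.1.2).

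- Readings: 6 × 22 = 132 under 7.7; 4 × 22 = 88 under the schedules. The difference, 132 − 88 = 44, is the post-dose readings.
- Pre/post pairs at subject level: 22 × 2 visits = 44 under 7.7; 22 × 0 = 0 under the schedules.
- Pre/post pairs at eye level: 44 × 2 = 88 under 7.7; 0 under the schedules.
- Baseline-to-final pairs: 22 under either source.
- With only the 18 subjects that 10.1.2 calculates before the allowance for losses: 18 × 2 = 36 pairs under 7.7; still 0 under the schedules.

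**Step 5. What depends on the missing cells.** The visit 1 and visit 2 contrast needs them and would lapse. The adverse-event rule compares with the baseline visit, so it still works at visit 1, visit 2 and the final visit. It could not register a loss present only in the post-dose window.

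**The case against.** The strongest reply is that little is lost. The secondary analysis is expressly conditional, so under the schedules the contrast lapses within the plan. Baseline against final survives in full. Pupil diameter, a primary variable, is measured after the drop in every schedule, and 7.4.5.4 treats a change above 2 mm as an adverse event. Adverse events are also assessed after the drop, with questioning, and 7.4.5.9 lists blurred vision and mydriasis as possible events. SAP 6.2.1 and 6.2.2 refer only to baseline-adjusted differences; the explicit visit 1 and 2 contrast is in the Protocol. There is one site, and its staff must be trained on the protocol. All of this stands, and it limits the size of the point.

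It is also fair that three schedules agree against one section, so deleting the item from 7.7 would restore consistency too. A post-dose reading would follow the anaesthetic and dyes used before the drop, and possibly dilation at the investigator's discretion, so it may not isolate the drug's effect. That is a reason to fix the order of tests. Post-dose staining and pupil diameter face some of the same interference, and the schedules keep them.

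Three stronger readings are tempting, and the documents do not support them.

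- A reader might infer that the BCVA analysis is lost. It is not: the baseline-to-final comparison remains, and a site following 7.7 has all the data.
- A reader might infer that acute visual effects would go undetected. What is missing is one quantitative measure; pupil diameter and adverse events are still assessed after dosing.
- A reader might take the sentence "Visual acuity will be measured in the study eye" in 7.4.5.6 to mean that half the treated eyes go unread. It describes testing one eye with the other covered. Eligibility in 5.1.1 requires adequate acuity in both eyes, and 10.1 appears to have each subject contribute both eyes. It is loose wording and a separate matter.

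**Conclusion.** The point holds as an inconsistency between the visit procedures and the schedules, at the level of a worthwhile correction. If the site follows the schedules, no BCVA reading falls in the 20–40 minute window, 0 of 44 subject-level pre/post pairs exist, and an acute loss of two or more lines would not be measured. If it follows 7.7, up to 44 pairs exist. The supported risk is inconsistent collection.

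The counts assume all 22 planned subjects attend both visits and that the site follows one source throughout; mixed practice would give a number in between. BCVA is outside the study hypothesis and the sample size calculation, so neither sample size nor error rates are affected.

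**What to change.** 1. Mark BCVA in the Post-Tx columns of visits 1 and 2 in Protocol 1.3, Protocol Table v and SAP Table 1, to match 7.7.2 and 7.7.3. This direction is preferred because 7.7 already asks for the test and the analysis in 10.3.2 can use it. If the omission was intended, the sponsor should say so, remove the item from the post-application lists, and limit the BCVA analysis to baseline against final.
2. State in Protocol 10.3.2.2 and SAP 6.2.2 that the BCVA contrasts are pre/post at visits 1 and 2, and baseline against the final visit.
3. As a separate wording correction, have 7.4.5.6 refer to each eye, since both are treated.

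The cost is edits to three tables and a few sentences. If the site had planned from the schedules, the extra reading adds a few minutes at each of two visits.
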